9.2.2 Method of Detecting AEs and SAEs

AEs can be spontaneously reported or elicited during open-ended questioning, examination, or evaluation of a subject. To prevent reporting bias, subjects should not be questioned regarding the specific occurrence of one or more AEs.

9.2.3 Follow-up of AEs and SAEs

- Nonserious AEs should be followed to resolution or stabilization or reported as SAEs if they become serious (see [APPENDIX 3](#)).
- Follow-up is also required for nonserious AEs that cause interruption or discontinuation of study treatment and for those present at the end-of-study treatment as appropriate.
- All identified nonserious AEs must be recorded and described on the nonserious AE page of the case report form (CRF). Completion of supplemental CRFs may be requested for AEs and/or laboratory abnormalities that are reported/identified during the course of the study.

After the initial AE/SAE report, the investigator is required to proactively follow each subject at subsequent visits/contacts. All SAEs and nonserious AEs of special interest (as defined in [Section 9.2.8](#)) will be followed until resolution, until the condition stabilizes, until the event is otherwise explained, or until the subject is lost to follow-up (as defined in [Section 8.3](#)).

Further information on follow-up procedures is given in [APPENDIX 3](#).

9.2.4 Regulatory Reporting Requirements for SAEs

- Prompt notification by the investigator to the Sponsor or designee of SAEs is essential so that legal obligations and ethical responsibilities toward the safety of subjects and the safety of a product under clinical investigation are met.
- An investigator who receives an investigator safety report describing SAEs or other specific safety information (eg, summary or listing of SAEs) from the Sponsor or designee will file it along with the IB and will notify the Institutional Review Board (IRB)/Independent Ethics Committee (IEC), if appropriate according to local requirements.

Sponsor or designee will be reporting AEs to regulatory authorities and ethics committees according to local applicable laws including European Directive 2001/20/EC and FDA Code of Federal Regulations 21 CFR Parts 312 and 320. A SUSAR is a subset of SAEs and will be reported to the appropriate regulatory authorities and investigators following local and global guidelines and requirements.

9.2.5 Pregnancy

If, following initiation of the study treatment, it is subsequently discovered that a participant is pregnant or may have been pregnant at the time of study exposure, including during and at least for 30 days after study product administration, the investigator must immediately notify the BMS Medical Monitor/designee of this event and complete and forward a Pregnancy Surveillance Form to BMS Designee within 24 hours of awareness of the event and in accordance with SAE reporting procedures described in [APPENDIX 3](#).

Follow-up information regarding the course of the pregnancy, including perinatal and neonatal outcome and, where applicable, offspring information must be reported on the Pregnancy Surveillance Form. Protocol-required procedures for study discontinuation and follow-up must be performed on the participant.

Any pregnancy that occurs in a female partner of a male study subject should be reported to Sponsor or designee. In order for the Sponsor or designee to collect any pregnancy surveillance information from the female partner, the female partner must sign an ICF for disclosure of this information. Information on this pregnancy will be collected on the Pregnancy Surveillance Form.

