5.1.2 Double-blind Treatment Period

At the Day 1 study visit, subjects who have completed the screening procedures and meet the eligibility criteria will be randomized in a 3:1 ratio to receive BMS-986165 12 mg BID or placebo BID PO, respectively for the 12-week double-blind treatment period. Randomization criteria are outlined in [Section 6.3](#). Subjects randomized to the 6 mg BID arm under the Original Protocol or Protocol Amendment 01 will continue to receive 6 mg BID for the 12-week double-blind treatment period and will receive 6 mg BID in the OLE period.

Prior to each scheduled visit, the subject diary should be reviewed to ensure SF and RB data have been entered daily. Prior to each scheduled visit at which Mayo scores are to be calculated, study personnel should ascertain whether an adequate number of days of diary entries have been made ([APPENDIX 9](#)). If adequate entries have not been made, the site should contact the subject to reschedule the visit to allow time for a sufficient number of daily diary entries for endpoint assessment, and the subject should be counseled about proper study procedures.

Endoscopy for the assessment of efficacy at Week 12 must occur in a window of 7 days prior to the Week 12 visit.

If a colonoscopy is performed during the screening visit, colonoscopy will be the preferred endoscopic procedure for subsequent endoscopies within the study. This approach will facilitate comparison between the individual colonic segments assessed at the screening visit and subsequent assessments.

Treatment discontinuation criteria are detailed in [Section 8.1](#). Subjects who **temporarily interrupt study treatment** will remain in the study and continue to participate in study procedures ([Section 8.1.1](#)).

Subjects who **permanently discontinue study treatment** will complete an **ET visit**. For subjects who permanently discontinue study treatment between Weeks 4 and 12, the ET visit will include an endoscopy. For subjects who permanently discontinue study treatment prior to Week 4, endoscopy at the ET visit is optional but encouraged. Subjects who permanently discontinue study treatment will be followed for protocol-specified posttreatment follow-up procedures. The only exception to this is when a subject specifically withdraws consent for any further contact with him/her or with persons previously authorized by the subject to provide this information (see [Section 8.2](#)).

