5.1.3 Open-label Extension Period

Subjects who are likely to derive a clinical benefit from ongoing participation in the study following Week 12, as judged by the investigator, are eligible to enter the OLE period. The OLE

period will last up to 40 weeks, to Week 52. Subjects will receive BMS-986165 6 mg BID PO during the OLE. There is no provision for dose escalation of IP during the OLE.

[REDACTED]

[REDACTED]

[REDACTED]

The symptomatic Mayo score at the Week 20 visit will be calculated using the **3 most recent (not necessarily consecutive) valid electronic subject diary entries recorded from the 7 days prior to the day of the study visit.**

[REDACTED]

Subjects who require any rescue therapy during the OLE period (Section 5.1.5) must permanently discontinue from study treatment (Section 8.1).

Endoscopy for the assessment of efficacy at Week 52 must occur in a window of 7 days prior to the Week 52 visit.

Endoscopy is required at the ET visit for subjects who permanently discontinue study treatment between Week 20 and prior to Week 52. Endoscopy is optional, but encouraged, for subjects who have an ET visit between Weeks 12 and 20.

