- Pregnancy, positive pregnancy test, or subject no longer wishes to comply with study requirements relating to prevention of pregnancy (Refer to [Section 9.2.5](#))

All subjects who discontinue study treatment should comply with protocol-specified ET and follow-up procedures as outlined in the Schedule of Activities ([Section 2](#)). The only exception to this requirement is when a subject withdraws consent for all study procedures including posttreatment study follow-up or loses the ability to consent freely (ie, is imprisoned or involuntarily incarcerated for the treatment of either a psychiatric or physical illness).

If study treatment is discontinued prior to the subject's completion of the study, the reason for the discontinuation must be documented in the subject's medical records and entered on the appropriate eCRF page.

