9 STUDY ASSESSMENTS AND PROCEDURES

Study procedures and timing are summarized in the Schedule of Activities ([Section 2](#)). Waivers or exemptions from protocol-required evaluations are not allowed.

All immediate safety concerns must be discussed with the BMS Medical Monitor/designee immediately upon occurrence or awareness to determine if the subject should continue or discontinue treatment.

Adherence to the study design requirements, including those specified in the Schedule of Activities (Section 2), is essential and required for study conduct.

All screening evaluations must be completed and reviewed to confirm that potential subjects meet all eligibility criteria before randomization. The investigator will maintain a screening log to record details of all subjects screened and to confirm eligibility or record reasons for screening failure, as applicable.

Procedures conducted as part of the subject's routine clinical management (eg, complete blood count) and obtained before signing of the ICF may be utilized for screening purposes provided the procedure meets the protocol-defined criteria and this approach has been discussed and agreed with the BMS Medical Monitor/designee (Section 2). A CXR performed less than 6 months prior to signing of the ICF may be used in place of the screening CXR, provided the subject has no symptoms or signs suggestive of pulmonary disease in the interim.

Assessments at the randomization visit (Day 1) must be performed per protocol. Standard of care assessments may not be used to establish pretreatment baseline parameters (ie, at the randomization visit). Procedures not specified in the protocol that are part of standard care may be performed if they do not interfere with study procedures. Any data arising from such procedures are not to be reported in the eCRF.

The study data includes all the information that is collected as a result of the study, including participant demographics, disease characteristics, clinical information, blood tests, biomarker tests, endoscopic videos, intestinal biopsies obtained during endoscopy, and other tests listed in

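### On the visible text, a subject stopped for pregnancy in Weeks 4-12, or from Week 20 to before Week 52, falls under a required endoscopy with biopsies, with no test of clinical need

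*Combined protocol and SAP*

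**What the plan says.** Section 8.1 lists the reasons for which study drug must be stopped. One is "Pregnancy, positive pregnancy test, or subject no longer wishes to comply with study requirements relating to prevention of pregnancy". It then says that all subjects who stop should complete the ET and follow-up procedures in the Schedule of Activities, and limits the exceptions: "The only exception to this requirement is when a subject withdraws consent for all study procedures including posttreatment study follow-up", or when she loses the ability to consent freely.

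Section 9.2.5, on a pregnancy found after treatment has started, says: "Protocol-required procedures for study discontinuation and follow-up must be performed on the participant". It also requires immediate notification of the Medical Monitor and a Pregnancy Surveillance Form with follow-up to the perinatal and neonatal outcome.

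What the ET visit contains depends on when treatment stops:

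- Double-blind period, Section 5.1.2: "For subjects who permanently discontinue study treatment between Weeks 4 and 12, the ET visit will include an endoscopy". Earlier than that: "For subjects who permanently discontinue study treatment prior to Week 4, endoscopy at the ET visit is optional but encouraged".
- Open-label extension, Section 5.1.3: "Endoscopy is required at the ET visit for subjects who permanently discontinue study treatment between Week 20 and prior to Week 52". Between Weeks 12 and 20 it is optional, with encouragement.

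Section 5.1 couples endoscopy with colonic biopsies at ET visits, and Tables 2 and 14 mark biopsies in the Week 52 end-of-treatment/ET column. Section 9 adds: "Waivers or exemptions from protocol-required evaluations are not allowed".

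**The concern.** Each rule is ordinary by itself. Read together, they place a subject whose pregnancy has just been found under a study endoscopy, with its bowel preparation and biopsies, and no visible text asks whether she needs it. The protocol applies a test of clinical indication to endoscopy at unscheduled visits (5.1). At entry it asks whether a bleeding disorder or anti-thrombotic use would preclude safe endoscopy and biopsy (6.2). It also excludes pregnant women at entry, so this ET visit is the one place where the visible text schedules a study endoscopy in a subject known to be pregnant.

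At stake are the subject's interests and a clear rule for the site. An investigator who decides against the procedure has to record a deviation or rely on general clauses that do not mention pregnancy. The opt-out that 8.1 names, withdrawal from all study procedures including follow-up, works against the pregnancy follow-up that 9.2.5 asks for.

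**Working it through.** The plan gives no figure on this point, so the check is mainly one of text, followed by the size of the windows and the effect on the primary analysis.

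1. **Is stopping mandatory?** Yes. Pregnancy and a positive test are both on the 8.1 list.

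2. **Does the ET endoscopy follow?** Yes in two windows, Weeks 4 to 12 (5.1.2) and Week 20 to before Week 52 (5.1.3). It is optional in Weeks 0 to 4 and 12 to 20.

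3. **Does the spacing rule exempt anyone?** Section 5.1 limits ET endoscopy in the double-blind period to visits at least 4 weeks after the last required endoscopy. The screening endoscopy precedes Day 1, and Week 4 is Day 29. The gap is therefore at least 29 - 1 = 28 days, or 4 weeks, and stops at or after Week 4 are not exempt. In the extension, the last required endoscopy is in the 7 days before the Week 12 visit, and 20 - 12 = 8 weeks.

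4. **Is there a visible exception?** The exceptions in 8.1 are consent-related. Section 9 rules out waivers. Section 9.2.5 has no carve-out. Notifying the Medical Monitor is a reporting duty; the visible text attaches no power to waive.

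5. **How much of the treatment period is covered?**
   - Double-blind: (12 - 4)/12 = 8/12 = 67%.
   - Extension: (52 - 20)/40 = 32/40 = 80%.
   - Both, for a subject who stays to Week 52: (8 + 32)/52 = 40/52 = 77%.
   - Optional: (4 + 8)/52 = 12/52 = 23%.

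   A subject who does not enter the extension faces only the 8 of 12 weeks. These are shares of calendar time, not of subjects or of risk.

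6. **Would sparing the endoscopy change the primary analysis?** Section 10.1.1 expects an exact 95% interval of (42%, 75%) at a response rate of about 60% in 37 subjects. With 22 responders, 22/37 = 59.5%. The Clopper-Pearson limits are the 2.5% point of Beta(22, 16) and the 97.5% point of Beta(23, 15), which give 42.1% and 75.2% and reproduce the plan. Under Section 10.4.1.1, a subject who stops treatment before Week 12 stays in the denominator and counts as a nonresponder whatever an ET endoscopy shows. Numerator, denominator and interval are the same with or without the procedure, so the change is 0.

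**The case against.** The strongest objection is redaction. Section 6.1 sends the reader to the Schedule of Activities for pregnancy testing during and after treatment, yet neither Table 1 nor Table 2 shows such a row. Both tables' abbreviation lists define women of childbearing potential, although no visible row or footnote uses the term, and some footnote letters are absent. The endoscopy paragraph in 9.1.1 breaks off. Pregnancy and endoscopy instructions are therefore probably among the withheld text. Because 8.1 requires ET procedures as the Schedule sets them out, a footnote there limiting the ET endoscopy would define the requirement and need not contradict the stated exceptions. This stands in full: the point holds for the visible text only.

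Second, the compulsion is softer than it first looks. Section 8.1 says subjects should comply, 9.2.5 does not name endoscopy, flexible sigmoidoscopy is allowed, and Appendix 2 permits deviation for an immediate hazard and puts subject well-being above science. This stands in part. A sensible investigator has room to act, but 9.2.5 uses mandatory wording and none of these clauses mentions pregnancy.

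Third, the group is small: women of childbearing potential within about 50 subjects of both sexes, using contraception and tested negative within 24 hours before the first dose. That is fair, and it is why this is an optional improvement.

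A reader might infer that the protocol forces an unsafe procedure on pregnant women. The documents say nothing about the risk of endoscopy in pregnancy, and the point does not depend on it. A reader might also infer that a subject who declines is dropped. No visible text says so, and Section 5.1.2 points the other way: "Subjects who permanently discontinue study treatment will be followed for protocol-specified posttreatment follow-up procedures".

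**Conclusion.** The point holds, limited to the visible text. For stops in 40 of 52 treatment weeks (77%), the stated rules include an ET endoscopy with biopsies after a pregnancy stop, with no step that asks about clinical need. Each affected subject means one procedure. No pregnancy rate is given, so no number of subjects is projected.

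The documents do not support the conclusion that the plan lacks any pregnancy condition, because the places where one would naturally sit are partly redacted. That a test of clinical need belongs here is a clinical judgment, although the protocol already applies the same test at unscheduled visits. The statistical reason to keep the procedure is weak: the primary estimate does not use it, and the Week 52 endpoints are exploratory (Table 3), with their analysis left to a SAP. This is a low-priority improvement, held with medium confidence.

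**What to change.** First check the unredacted Schedule of Activities and Section 9.1.1. If a pregnancy condition on the ET endoscopy is already there, a cross-reference from 9.2.5 is enough.

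If not, at the next amendment:

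- **Section 9.2.5:** add that the ET endoscopy, bowel preparation and biopsies are not required, and in the optional windows not encouraged, unless clinically indicated, in a subject discontinued for pregnancy, or for a positive test until pregnancy is excluded. State that all other ET, safety, follow-up and Pregnancy Surveillance Form requirements still apply. The serum test that Section 6.1 uses after an ambiguous urine result could serve to exclude pregnancy.
- **Sections 8.1 and 9:** name this exception in the sentence that limits exceptions and in the sentence that bars waivers. Cross-references alone would leave both in conflict with the new text.
- **Sections 5.1.2 and 5.1.3:** add a cross-reference to 9.2.5.

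The cost is one added provision, two amended sentences and two cross-references. One exploratory ET endoscopy with its biopsies is not obtained per affected subject, and the primary analysis is unchanged.

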9.2.6 Laboratory Test Result Abnormalities

The following laboratory test result abnormalities should be captured on the nonserious AE CRF page or SAE Report Form electronic, as appropriate. Paper forms are only intended as a back-up option when the electronic system is not functioning.

- Any laboratory test result that is clinically significant or meets the definition of an SAE
- Any laboratory test result abnormality that required the participant to have study treatment discontinued or interrupted
- Any laboratory test result abnormality that required the participant to receive specific corrective therapy

It is expected that wherever possible, the clinical rather than laboratory term would be used by the reporting investigator (eg, anemia versus low hemoglobin value).

9.2.7 Potential Drug-Induced Liver Injury (DILI)

Clinical chemistry and coagulation tests will be assessed as indicated in the Schedule of Activities ([Section 2](#)). Subjects with abnormal liver blood tests should be further assessed to determine if these meet the criteria for discontinuation of the study drug (see [Section 8.1](#)) or the criteria for potential DILI.

Potential DILI is defined as:

- 1) ALT or AST elevation $> 3 \times$ ULN,
AND
- 2) Total bilirubin $> 2 \times$ ULN, without initial findings of cholestasis (elevated serum alkaline phosphatase),
AND
- 3) No other immediately apparent possible causes of ALT or AST elevation and hyperbilirubinemia, including, but not limited to, viral hepatitis, preexisting chronic or acute liver disease, or the administration of other drug(s) known to be hepatotoxic.

Identification of a clinically significant elevation(s) in liver-related chemistry or coagulation tests (including those defined in [Section 8.1](#), or meeting the definition for potential DILI) should be followed by repeat testing of ALT, AST, total bilirubin, ALP, and INR within 48-72 hours to: (1) confirm the abnormalities, and (2) determine if they are increasing or decreasing.

Investigators should consult with the BMS Medical Monitor/designee immediately if a subject meets the laboratory criteria for potential DILI.

Investigators should consider gathering additional clinical information and laboratory and imaging tests to seek other possible causes of the observed liver blood test abnormalities, including (but not limited to) acute viral hepatitis, alcoholic and autoimmune hepatitis, biliary obstruction (small and large duct), cardiovascular causes (eg, ischemic hepatitis), nonalcoholic steatohepatitis (NASH), and the effect of concomitant treatments.

A review of all concomitant medications should include herbal medicines, dietary supplements, nonprescription OTC medications, including acetaminophen/paracetamol, and occupational exposure to chemical agents.

Wherever possible, timely confirmation of initial liver-related laboratory abnormalities should occur prior to the reporting of a potential DILI event. All occurrences of potential DILIs, meeting the defined criteria, must be reported as SAEs (see [Section 9.2](#) and [APPENDIX 3](#) for reporting details). All subjects with clinically significant abnormalities in liver-related blood tests, or potential DILI, must be followed until all abnormalities return to normal or to the baseline state.

9.2.8 Adverse Events of Interest (Clinical Safety Program)

All AEs and SAEs that arise in the study will be reported and investigated. However, because of the characteristics of the disease under study, and BMS-986165 in particular, some AEs are considered adverse events of interest (AEIs). AEIs may be serious or nonserious. Such events may require further investigation to better characterize and understand them.

In addition, given that immunosuppression is consistent with the mechanism of action of BMS-986165, malignancies are considered to be an important potential risk of therapy with BMS-986165 and will be monitored as AEs. Malignancies were not identified as adverse findings in nonclinical studies and no serious adverse reactions of malignancy have been reported to date in clinical studies of BMS-986165.

Additional information on AEs will be collected in this study. Reporting of an AE or SAE that includes a PT that is linked to an AEI will trigger specialized eCRF pages to collect additional information related to characterization, social/family history, risk factors, signs/symptoms, diagnostics, and treatments. Additional information may also be requested to aid in the evaluation of these AEs.

9.2.9 Other Safety Considerations

Any significant worsening noted during interim or final physical examinations, ECG, x-ray filming, any other potential safety assessment required or not required by protocol should also be recorded as a nonserious AE or SAE, as appropriate, and reported accordingly.

